4.2.2 Handling of missing data for AE

For analyses of AEs, a complete date must be established in order to correctly identify the AE as occurring during treatment or not. For purposes of imputing missing components of partially-reported start and stop dates for AEs, the algorithms listed below will be followed. Start and stop dates of AEs will be displayed as reported in the subject data listings (ie, no imputed values will be displayed in data listings).

Partial AE start dates will be imputed as follows:

Imputation of Partial Start Dates:

- If only the month and year are specified and the month and year of first dose is not the same as the month and year of the start date and the subject did not switch treatment during that month and year, then use the 1st of the month.
- If only the month and year are specified and the month and year of first dose is the same as the month and year of the start, then use the date of first dose.
- If only the month and year are specified and the subject did switch treatment during that month and year, then use the date of first switch treatment.
- If only the year is specified, and the year of first dose is not the same as the year of the start date and the subject did not switch treatment during that year, then use the 1st of January of the year of the start date.
- If only the year is specified, and the year of first dose is the same as the year of the start date, then use the date of first dose.
- If only the year is specified, and the year of first dose is the same as the year the subject did switch treatment, then use the date of first switch treatment.
- If only the year is specified, and the year of first dose is the same as the year of the start date and the same as the year the subject did switch treatment, then use the date of first dose.
- If the start date is completely unknown and the stop date is unknown or not prior to the date of first dose, then use the date of first dose.

If the date of first study medication or switch treatment is partial, then the above imputation approach will be applied:

- If only the day of first study medication or switch treatment administration is unknown, then this will be set to either the first of the month, or the day of first treatment allocation visit (excluding placebo run-in), whichever is later.
- If both the day and month of first study medication or switch treatment are unknown, then this date will be imputed to be the date of first treatment allocation visit.

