10.2 Adverse events

An AE is any untoward medical occurrence in a patient or clinical investigation subject administered a pharmaceutical product that does not necessarily have a causal relationship with this treatment. An AE can therefore be any unfavorable and unintended sign (including an abnormal laboratory finding), symptom, or disease temporally associated with the use of a medicinal (investigational) product, whether or not related to the medicinal (investigational) product.

AEs (including serious AEs) are characterized as either non-treatment or treatment emergent according to the following criteria:

- Non-treatment emergent are the events with onset date and time prior to the very first administration of study medication (bimekizumab or placebo) or after a 140-day period after the final drug administration.
- Treatment-emergent AEs (TEAE) are those with onset date at or after the very first administration of study medication. The events that emerge within 140 days after the final drug administration, will also be considered as treatment emergent (eg, in the case of premature discontinuation or during the Safety Follow-up [SFU] period).

All AEs occurring during the study (i.e., after signature of the informed consent document) will be recorded in the eCRF. For each AE the following information will be recorded in the eCRF: AE term (verbatim term), date of onset, whether or not the AE was classified as a SAE, as an AE of special interest, intensity, relationship to study medication, action taken with study medication, other action taken, outcome, date of outcome, and whether the AE led to study drug discontinuation or to study discontinuation.

ADRs are defined as a response to a drug which is noxious and unintended and which occurs at doses normally used in man for prophylaxis, diagnosis, or therapy of disease or for modification of physiological function. Any AE that is considered "Related" to study treatment will be classed as an ADR.

If an AE occurs on the same day as the treatment switch (Visit 7, Week 12) then the AE will be allocated to the Double-Blind treatment. An exception from this general rule is made for ADRs, and AE of hypersensitivity reactions and anaphylactic reactions. If those AEs occur on the same days as the treatment switch, the AEs will be allocated to the Dose-Blind treatment.

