The incidence of TEAEs will be summarized by MedDRA SOC, high level term, and PT. Tables with incidences of classified TEAEs by maximum intensity, by relationship, and by subject number will be provided. The incidence of non TEAEs, non-serious TEAEs above the reporting threshold of 5% of subjects and relationship will be summarized. Furthermore the incidence of all TEAEs, serious TEAEs, non-serious TEAEs, and TEAEs leading to study discontinuation and/or permanent withdrawal of study medication, adverse drug reactions, fungal infectious disorder TEAEs, opportunistic infection (including tuberculosis) TEAEs, malignant or unspecified tumor TEAEs, malignant tumor TEAEs, major cardiovascular event TEAEs, haematopoietic cytopenias TEAEs, neuropsychiatric events TEAEs, inflammatory bowel disease TEAEs, hypersensitivity and anaphylactic Reaction TEAEs, hepatic events TEAEs, and TEAEs by timing of onset relative to AbAb Status will be summarized. In addition, an overall summary table will be provided.

The tables will be split into the Double-Blind Period and the complete treatment period (exception non TEAE table and TEAEs by timing of onset relative to AbAb Status).

Presentations for the Double-Blind Period will summarize AEs that start prior to or at Visit 7 (see details given above) by treatment group as randomized for the Double-Blind Period.

Presentations for the complete treatment period will only summarize AEs that occur under treatment with bimekizumab, irrespective of the treatment period. For summaries of the bimekizumab 160mg, 160mg with loading dose and bimekizumab 320mg treatment groups, patients randomized to Placebo or bimekizumab 16mg at Baseline will only be included with AEs that start in the Dose-Blind Period. The all bimekizumab treatment group will also present AEs occurring under bimekizumab 16mg treatment in the Double-Blind Period. AEs for each subject will be summarized based on the treatment actually received at the onset of each particular AE.

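### Adverse events judged not related, with an onset imputed to the Week 12 switch date, are always credited to placebo or 16mg, and the year-only rule never tests the event's own year

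*SAP*

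**What the plan says.** **Imputing the date (SAP 4.2.2).** A start date with only month and year becomes the 1st of the month, with two exceptions. In the month of first dose it becomes the first-dose date. In the month of the switch, where "the subject did switch treatment during that month and year, then use the date of first switch treatment" applies, it becomes the switch date.

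**Allocating the event (SAP 10.2).** The general rule covers any AE that "occurs on the same day as the treatment switch (Visit 7, Week 12) then the AE will be allocated to the Double-Blind treatment". The SAP then adds: "An exception from this general rule is made for ADRs, and AE of hypersensitivity reactions and anaphylactic reactions". For these, "the AEs will be allocated to the Dose-Blind treatment". An ADR is any AE judged related, and 4.2.2 counts a missing relationship as related. SAP 4.3.1 has the same switch-day rule for the Week 12 interim analysis.

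**Tabulating the event (SAP 10.2 and 10.2.2).** Double-Blind tables take AEs that start up to and including Visit 7. "Presentations for the complete treatment period will only summarize AEs that occur under treatment with bimekizumab, irrespective of the treatment period". Subjects first randomized to placebo or 16mg enter the 160mg and 320mg columns only with AEs that start in the Dose-Blind Period. The All bimekizumab column also keeps AEs under 16mg. The exposure-adjusted incidence and event rates (EAIR, EAER) exist only for the complete treatment period.

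**Year-only dates (SAP 4.2.2, sixth start-date rule).** "If only the year is specified, and the year of first dose is the same as the year the subject did switch treatment", the switch date is used. SAP 4.2.3 repeats this rule for medications.

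**The concern.** A special rule for the switch month makes sense only if it changes something, and the natural purpose is to give an event of uncertain timing to the new treatment. The switch-day rule undoes that. For an AE judged not related, the switch date leads to the same arm as the 1st of the month would.

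The switch-day rule is reasonable for an observed date, because Week 12 assessments precede dosing. An imputed date carries no information that onset came before the dose, and nothing in 10.2 separates observed from imputed dates.

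At stake is the allocation of unrelated AEs in the tables of all TEAEs, serious TEAEs, TEAEs leading to discontinuation and special-monitoring TEAEs. For a former placebo subject the event disappears from the EAIR and EAER numerators, while that subject's bimekizumab time stays in the denominators (SAP 10.1 and 10.2.2).

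The year-only rule raises a different problem: a programmer cannot apply it as written without choosing between conflicting results.

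**Working it through.** The plan states no figure on this point, so there is none to reproduce.

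**Step 1. Who is exposed to the rule.** SAP 2.4 plans 40 subjects per group. Placebo and 16mg are rerandomized at Week 12: 40 + 40 = 80 of 200 planned subjects. This is the population at risk, not a count of events.

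**Step 2. Does the first-dose rule intervene?** The switch is planned at day 84 with a window of 3 days either way (protocol section 8), so 81 to 87 days after first dose. No month is that long, so first dose and switch never share a month. A month-only AE in the switch month always receives the switch date.

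**Step 3. Where such an AE goes.**

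| AE with onset imputed to switch date | Former placebo | Former 16mg |
|---|---|---|
| Related, relationship missing, hypersensitivity or anaphylactic | Dose-Blind treatment | Dose-Blind treatment |
| Any other AE | Placebo; absent from all bimekizumab columns, EAIR and EAER | 16mg; absent from 160mg/320mg, kept in All bimekizumab |

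**Step 4. How much of the switch month lies after the switch.** For a switch on day d of a month with L days, the share of days strictly after is (L − d)/L. Summed over d, one month gives (L − 1)/2. Averaged over every switch day of a 365-day year:

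- mean = [(365 − 12)/2]/365 = 176.5/365 = 0.4836, or about 48%
- minimum = 0 (switch on the last day of the month)
- maximum = 30/31 = 0.968, or about 97% (switch on the 1st of a 31-day month)
- on or before the switch, on average = 1 − 0.4836 = 0.5164, or about 52%

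This assumes switch days spread evenly over the calendar. Reading it as a share of events also assumes onset is even within the month.

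**Step 5. The year-only rules applied to example dates.** The fourth rule gives 1 January of the AE year when neither first dose nor switch fell in that year. The fifth gives first dose when the AE year is the first-dose year. The sixth gives the switch date when first-dose year equals switch year. The seventh gives first dose when all three years agree.

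| AE year | First dose | Switch | Rules met and result |
|---|---|---|---|
| 2018 | 1 Jun 2017 | 24 Aug 2017 | 4th: 1 Jan 2018; 6th: 24 Aug 2017 (wrong year) |
| 2016 | 10 Jan 2017 | 4 Apr 2017 | 4th: 1 Jan 2016; 6th: 4 Apr 2017 (wrong year, becomes treatment-emergent) |
| 2017 | 1 Mar 2017 | 24 May 2017 | 5th and 7th: 1 Mar 2017; 6th: 24 May 2017 |
| 2017 | 15 Nov 2016 | 7 Feb 2017 | none |

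No order of precedence is given. The third row is the mildest conflict, since the seventh rule can be read as overriding the sixth. The fourth row needs a first dose in the last 84 days of a year: 84/365 = 23% of possible first-dose dates.

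**The case against.** Several points on the other side stand.

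- **Scope.** A reader might infer that every AE with a partial date goes to the earlier arm. The SAP does not say that. A completely unknown start date goes to first dose unless the stop date precedes it. A year-only date in the first-dose year also goes to first dose under the fifth and seventh rules. Related events and hypersensitivity or anaphylactic reactions follow the new treatment.
- **The plan's worst-case stance.** One might say the rule defies it throughout. For relationship it does not: a missing relationship counts as related and so falls under the exception. The SAP also treats an ambiguous AE as treatment-emergent. That settles emergence but not which treatment, so it does not cure the problem.
- **Direction.** A reader might infer a bias that always favours bimekizumab. The documents do not support this. About 52% of switch-month days fall on or before the switch, so under even onset the present allocation is right about as often as wrong. The year-only rule can also move a pre-treatment AE on to treatment.
- **Loss from bimekizumab rates.** This holds for former placebo subjects only, because 16mg is bimekizumab and its events stay in All bimekizumab.
- **Literal reading.** SAP 4.2.2 presents its rules as filling in missing date components. A recorded year is not missing, so replacing it contradicts that purpose, and the sixth rule is probably a drafting slip. It is still the text a programmer must implement.
- **Frequency.** AEs are prompted at every visit (protocol 12.1.4), with visits at Weeks 8, 12 and 16, so year-only onsets near the switch should be rare.

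None of this resolves the conflict between 4.2.2 and 10.2 for an imputed date.

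**Conclusion.** The point holds in a limited form. For AEs judged not related, and not hypersensitivity or anaphylactic reactions, imputing onset to the switch date has no effect on allocation, because the switch-day rule returns the event to placebo or 16mg every time. On average about 48% of the switch month's days fall after the switch (0% to 97% by switch day), so a material share of such events may have begun on the new treatment. The sixth start-date rule is separately defective as written: it can give a date in the wrong year, it conflicts with the fourth rule, and it leaves an AE in the switch year uncovered when first dose was in the previous year.

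The number of events cannot be derived, because the documents give no rate of partial dates; it is likely small. The primary efficacy analysis is untouched, and AE reporting is largely descriptive. Correction is worthwhile because the rules misfire as stated and the change is cheap, not because a large bias has been shown.

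**What to change.** 1. In SAP 10.2 add: *If the onset date was imputed to the switch date, the AE is allocated to the Dose-Blind treatment, unless a known stop date is before the switch.* Report the number of AEs allocated this way. Imputing to the day after the switch is not a good alternative: when the switch falls on the last day of a month, it puts the AE in a month that contradicts the recorded one.
2. In SAP 4.2.2, replace the condition of the sixth start-date rule by: *the year of the start date is the year of the switch and not the year of first dose.* Make the same change in 4.2.3. Each example in the working then has a single result: 1 Jan 2018, 1 Jan 2016, 1 Mar 2017 and 7 Feb 2017.

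The cost is one added sentence, one replaced condition in two sections, and a small derivation change. The allocation in item 1 is conservative, not unbiased: some events that began before the switch will move to bimekizumab, and its AE rates may rise slightly. The reported count lets a reader judge how much this matters.

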4.2.3 Handling of missing data for prior and concomitant medication

Any medications with incomplete start and end dates/times will be handled according to the following rules for classification as prior and concomitant. Such imputations will only be performed for these classifications and calculations; in the listings all data will be shown as recorded on the electronic case report form (eCRF).

Imputation of partial start dates:

- If only the month and year are specified and the month and year of first dose is not the same as the month and year of the start date and the subject did not switch treatment during that month and year, then use the 1st of the month.
- If only the month and year are specified and the month and year of first dose is the same as the month and year of the start, then use the date of first dose.
- If only the month and year are specified and the subject did switch treatment during that month and year, then use the date of first switch treatment.
- If only the year is specified, and the year of first dose is not the same as the year of the start date and the subject did not switch treatment during that year, then use the 1st of January of the year of the start date.
- If only the year is specified, and the year of first dose is the same as the year of the start date, then use the date of first dose.
- If only the year is specified, and the year of first dose is the same as the year the subject did switch treatment, then use the date of first switch treatment.
- If only the year is specified, and the year of first dose is the same as the year of the start date and the same as the year the subject did switch treatment, then use the date of first dose.

- If only the year is specified and the end date is before date of first dose, then set the start date to the 1st of January of the year of the start date.
- If only the year and day are specified and month is missing, then only the year will be considered and the month and day will be imputed with the rules above
- If the start date is completely unknown and the stop date is unknown or not prior to the date of first dose, then use the date of first dose.
- If the start date is completely unknown and the stop date is prior to the date of first dose, then set the start date to the 1st of January of the year of the end date.

If the date of first study medication or switch treatment is partial, then the above imputation approach will be applied:

- If only the day of first study medication or switch treatment administration is unknown, then this will be set to either the first of the month, or the day of first treatment allocation visit (excluding placebo run-in), whichever is later.
- If both the day and month of first study medication or switch treatment are unknown, then this date will be imputed to be the date of first treatment allocation visit.

Imputation of Partial Stop Dates:

- If only the month and year are specified, then use the last day of the month,
- If only the year is specified, then use December 31st of that year.
- If the stop date is completely unknown, do not impute the stop date.

There will be no imputation of any other missing data.

4.3 Interim analysis and data monitoring

Two interim analyses are planned for the study after the subjects have completed 12 and 48 weeks.

4.3.1 Interim analysis Week 12

After all enrolled subjects have completed the 12 weeks Double-Blind Period, an interim analysis will be performed (i) to analyze the dose:exposure response for ACR and PASI response criteria to determine the optimal therapeutic dose(s) for subsequent studies, and (ii) to perform a comprehensive evaluation of all Double-Blind data of the study.

No separate SAP for the interim analysis will be provided. The interim analysis is a limited version of the final analysis and will focus on specific topics, eg, primary and secondary efficacy analysis and comprise the results of the 12 weeks Double-Blind Period. The TFL shells for the interim and final analysis will be provided in two different documents.

The interim analysis will summarize disposition, demographics, PsA history, Baseline characteristics, PsA concomitant medication, efficacy analysis, AEs and treatment-emergent AEs (derivation [Section 10.2](#)), hematology and biochemistry laboratory data, and Electronic Columbia-Suicide Severity Rating Scale (eC-SSRS). Not all collected hematology and biochemistry laboratory variables will be summarized. For the interim analysis only selected

hematology and biochemistry variables will be provided as listed in [Table 12–4](#). Listings of AEs, hematology, biochemistry and C-SSRS data will be provided.

The interim efficacy analysis will focus on the primary and secondary efficacy analyses including supportive and sensitivity analysis. In addition, summary tables for the primary and secondary efficacy variables, the ACR components, and MDA will be provided. Categorical variables will be summarized using frequency tables by each visit. Categorical variables will be summarized using frequency tables by each visit. Continuous variables will be summarized using descriptive statistics by each visit. Time to onset of ACR50 response and ACR20 response will be summarized and plotted as described in [Section 8.3](#).

PK and AbAb data will be analyzed in the interim analysis as described in [Section 9.1](#) and [Section 9.2](#). Biomarker data will not be analyzed in the interim analysis.

The interim analysis includes selected data up to Week 12 and in addition data up to Week 24. The data up to Week 24 may include partial results up to the time the database for Week 12 was locked for ongoing subjects. Following variables will be analyzed: primary and secondary efficacy variables, ACR components, MDA, PK, AbAb, TEAEs, biochemistry and hematology laboratory results, and Hy's Law. It depends on the variable how those additional time points will be presented in the interim analysis.

The efficacy analyses and the plasma concentration analyses for the period between Week 12 and Week 24 are only for those treatment groups that are not rerandomized. Two summary tables for each of the primary and secondary efficacy variables, the ACR components, and MDA will be presented. The first table will include data up to Week 12 by treatment group at Baseline. The second table will include data up to Week 24 by the following treatment groups: bimekizumab 160mg and bimekizumab 160mg with loading dose 320mg, and bimekizumab 320mg. The summary table for plasma concentration will present only data up to Week 12 for the Baseline treatment groups Placebo and bimekizumab 16mg. Data up to Week 24 will be presented for bimekizumab 160mg, bimekizumab 160mg with loading dose 320mg, and bimekizumab 320mg. All Listings which include data up to Week 24 will use the same approach as for plasma concentration tables.

The safety analysis (TEAEs, biochemistry and hematology laboratory results, and Hy's Law) will be handled as follows: Two summary tables for each of the safety analysis will be presented. The first table will include data up to Week 12 by treatment group at Baseline. The second table will include data up to Week 24 and will also present subjects under their Baseline treatment group. For the second table any event/finding that is unique to a treatment group should only be presented in the "All subjects" column and the treatment columns should remain blank. Following rules will be applied for the TEAEs: If the relative TEAE start date is less or equal to 84 (12*7) days, then the TEAE will be presented in the up to Week 12 table. If the relative start date is less or equal to 168 (24*7) days, then the TEAE will be presented in the up to Week 24 table.

The treatment group information will not be displayed for the interim listings.

If an AE occurs on the same day as the treatment switch (Visit 7, Week 12) then the AE will be allocated to the Double-Blind treatment. An exception from this general rule is made for adverse drug reactions (ADRs), and AE of hypersensitivity reactions and anaphylactic reactions. If those

AEs occur on the same days as the treatment switch, the AEs will be allocated to the Dose-Blind treatment and will not be presented for the interim analysis.

Exposure of study medication will not be summarized but a listing will be provided including following information: date of first dose, date of last dose, and duration of exposure. The last dose for the Double-Blind Period is planned on Visit 6 (Week 8).

For the interim analysis, the database will be locked and the treatment codes will be made available to UCB personnel with exception of operational staff working on the study. An interim report will be written. The Investigators and subjects will remain blind to the assigned bimekizumab dosing regimen until the subject completes the Dose-Blind Period at Week 48. Further details are available in the PA0008 blinding plan.

Safety data will be provided to an independent Data Monitoring Committee (DMC). The DMC will review those safety data periodically. The composition and operation of the DMC will be defined in the DMC charter. The presentation and analysis of data for the DMC meetings is described within a separate DMC SAP.

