Investigational medicinal product (IMP) will be administered sc in the clinic at Baseline, Week 4, and Week 8. Additional non-dosing study visits in the Double-Blind Period will occur at Week 1 and Week 2. At Week 12, subjects will transition from the Double-Blind Period into the 36-week Dose-Blind Period. Note that the other assessments are planned to be performed before the IMP administration and will be analyzed for the Double-Blind Period.

Dose-Blind Period

The first IMP for the Dose-Blind Period will be administered at Week 12. At the Week 12 Visit, subjects will be allocated to bimekizumab treatment regimens as follows:

- Subjects in the placebo group will be rerandomized 1:1 to bimekizumab 160mg or bimekizumab 320mg Q4W

-
- Subjects in the bimekizumab 16mg dose group will be rerandomized 1:1 to bimekizumab 160mg or bimekizumab 320mg Q4W
 - Subjects in the bimekizumab 160mg dose group will continue to receive bimekizumab 160mg Q4W
 - Subjects in the bimekizumab 320mg dose group will continue to receive bimekizumab 320mg Q4W
 - Subjects in the bimekizumab 320mg (loading)/160mg dose group will continue to receive bimekizumab 160mg Q4W

All assessments for the Dose-Blind Period will be done from Week 18 to Week 48. The last IMP administration is on Week 44.

The total duration of treatment is 36 weeks.

During the 36-week Dose-Blind Period, subjects will be evaluated for inadequate response to treatment at defined time points. Subjects who do not show an improvement in tender and swollen joint count will be eligible to receive rescue therapy as defined in [Section 6.5](#).

Safety Follow-up/Extension study

At the completion of the Dose-Blind Period, Investigators should discuss treatment options with the subject. Subjects will be given the opportunity to enter an extension study at Week 48, provided they do not qualify for rescue therapy.

Table 2-1: Schedule of assessments

Protocol activity	Visit ^a / Week	Screening (V1) (14-28 days)	Baseline (Day 1, V2) (first dose)	Double-Blind Period (weeks after first dose)			Dose-Blind Period (weeks after first dose)						SFU ^b							
				3	4/5/6/8	7/12	9/	1/1/2/2/4	1/2/3/3/6	1/4/4/0	16/48	ET								

k It is recommended that Quantiferon TB GOLD test be performed.

l At Weeks 16, 24, and 36, subjects will be evaluated for inadequate response to treatment. Subjects who do not show an improvement in tender and swollen joint counts will be eligible to receive rescue therapy.

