3.7 Treatment assignment and treatment groups

It is expected that subjects receive treatment as randomized and hence safety analyses will be based on the SS, as randomized. However, if after unblinding it is determined that subjects randomized to placebo received bimekizumab at any time, then for safety analyses these subjects will be reallocated to the appropriate bimekizumab treatment group. Subjects randomized to bimekizumab will only be reallocated to the placebo treatment group if they did not receive bimekizumab at any time during the study.

Depending on the analysis sets, subjects will be summarized and listed based on the actual received treatment or according to the randomization which will be considered as planned treatment:

- All subjects screened/ES: planned treatment
- RS: planned treatment
- SS: actual treatment
- FAS: planned treatment
- PPS: planned treatment
- PK-PPS: actual treatment
- PD-PPS: actual treatment
- DBS: planned treatment (demographics, baseline characteristics, and efficacy analyses) or actual treatment
- ESS: planned treatment
- DBRS: planned treatment
- cESS: planned treatment
- cDBRS: planned treatment

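### The interim up-to-Week-24 safety tables keep switched subjects under their Baseline arm, so up to half of the follow-up in the placebo and 16mg columns is on bimekizumab 160mg or 320mg

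*SAP*

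**What the plan says.** SAP 2.3 sets the switch. "Subjects in the placebo group will be rerandomized 1:1 to bimekizumab 160mg or bimekizumab 320mg Q4W". The 16mg group follows the same rule: "Subjects in the bimekizumab 16mg dose group will be rerandomized 1:1 to bimekizumab 160mg or bimekizumab 320mg Q4W". On timing: "The first IMP for the Dose-Blind Period will be administered at Week 12".

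SAP 4.3.1 then sets the interim safety displays. "The safety analysis (TEAEs, biochemistry and hematology laboratory results, and Hy's Law) will be handled as follows": a first table up to Week 12 by Baseline arm, and a second to Week 24. "The second table will include data up to Week 24 and will also present subjects under their Baseline treatment group". An adverse event enters the first table under this condition: "If the relative TEAE start date is less or equal to 84 (12*7) days". The second table uses 168 days in the same way. The section adds that data after Week 12 may be incomplete at the lock, and that a finding seen in only one arm is shown only in the all-subjects column.

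Three other places bear on the choice:

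- For efficacy and plasma concentration, SAP 4.3.1 itself leaves the rerandomized arms out after Week 12.
- SAP 10.2, on the complete treatment period, says: "AEs for each subject will be summarized based on the treatment actually received at the onset of each particular AE".
- SAP 3.7 lists "SS: actual treatment", although its text also says that safety analyses use the Safety Set as randomized.

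SAP 4.3.1.1 records that the interim adverse-event tables were produced as described, with a change to the first table only.

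**The concern.** In the second table, an adverse event at Week 18 in a former placebo subject who now receives 320mg is counted in the placebo column. A similar event in a former 16mg subject is counted in the lowest-dose column. The label is then wrong for part of the follow-up, and no reason is given for treating safety differently from efficacy and plasma concentration in the same section.

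A reader of the interim output cannot easily separate the two periods. Exposure is listed but not summarized, exposure-adjusted rates are reserved for the final analysis, and the interim listings omit the treatment group. The Week 24 listings follow the plasma-concentration approach, which stops the placebo and 16mg groups at Week 12, so post-switch events can be in the table and absent from the listing. The rule for events on the day of the switch also sits oddly beside the table. A drug reaction on that day is assigned to the Dose-Blind treatment and left out of the interim, while the same reaction a day later falls under the Baseline arm.

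At stake is how this one table reads: a drug-related event can look like background in the placebo column, and a difference between 16mg and the higher doses can look smaller than it is.

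**Working it through.** **1. The cut-offs.** 12 × 7 = 84 and 24 × 7 = 168, as SAP 4.3.1 states. With the first dose as day 1 (SAP 3.2.1), the nominal Week 12 injection falls on day 85. Post-switch time in the second table is 168 − 85 + 1 = 84 days. With the ±3 day visit window (Protocol section 8) the switch falls on days 82 to 88, which gives 87 to 81 days.

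**2. Rate ratio.** Let r0 be the event rate under the column label, r1 the rate on 160mg or 320mg, each constant, and f the fraction of the Week 12 to 24 time available at the lock.

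- Displayed rate in the switched column = (12·r0 + 12·f·r1) / (12 + 12·f).
- If r1 = 2·r0, the displayed ratio = 2(1 + f) / (1 + 2f).
- Share of that column's time after the switch = f / (1 + f).

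| f | Share after switch | Ratio of 2.0 reads |
|---|---|---|
| 0 | 0% | 2.00 |
| 0.25 | 20% | 1.67 |
| 0.50 | 33% | 1.50 |
| 0.75 | 43% | 1.40 |
| 1.00 | 50% | 1.33 |

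At f = 1 the rate difference is halved. The same algebra applies to the 16mg column, with r0 as the 16mg rate.

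**3. Crude incidence, full follow-up.** Let p0 and p1 be assumed 12-week incidences on placebo and on drug.

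- Placebo throughout: 1 − (1 − p0)².
- Drug throughout: 1 − (1 − p1)².
- Placebo column as displayed: 1 − (1 − p0)(1 − p1).

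| p0, p1 | Placebo throughout | Displayed placebo | Drug | Difference: unmixed, then displayed |
|---|---|---|---|---|
| 5%, 10% | 9.75% | 14.5% | 19.0% | 9.25, then 4.5 points |
| 10%, 20% | 19.0% | 28.0% | 36.0% | 17.0, then 8.0 points |
| 20%, 40% | 36.0% | 52.0% | 64.0% | 28.0, then 12.0 points |
| 40%, 50% | 64.0% | 70.0% | 75.0% | 11.0, then 5.0 points |

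In these cases 43% to 49% of the unmixed 24-week difference remains. The share kept is (1 − p1) / [(1 − p0) + (1 − p1)], which is below one half whenever p1 exceeds p0.

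**4. The tempting remedy.** Suppose the placebo column stopped at Week 12, the other columns ran to Week 24, and crude percentages were kept. In the first row the table would show 5% against 19.0%, a gap of 14.0 points. That overshoots 9.25 by 4.75 points, exactly the size of the shrinkage (9.25 − 4.5 = 4.75). Truncation therefore needs time at risk beside it.

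**The case against.** The strongest reply is that the placebo comparison sits elsewhere in the same report. The first table covers the period up to Week 12 by Baseline arm and, as produced for adverse events, shows all events of the Double-Blind Period (SAP 4.3.1.1). The Week 24 table is a supplement, possibly partial, with no test attached. No arm stays on placebo after Week 12, so the unmixed 24-week figure is one this design cannot observe. The final tables already handle the switch: SAP 10.2 attributes events to the treatment at onset, and SAP 10.2.2 starts a former placebo subject's exposure at the first bimekizumab dose. All of this stands, and it limits the point to one display.

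The appeal to SAP 3.7 is also weaker than it looks. Its reallocation rule covers dosing that departs from randomization, not a planned switch, and the 10.2 sentence belongs to the complete-treatment-period tables. The Week 24 table is inconsistent in approach with those sections, but it does not plainly break a rule that governs it.

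Two defences do not stand. The single-arm rule does not cure the mixing: an event in one 320mg subject and one former placebo subject after the switch appears in both columns. Blinding may be the motive, but SAP 4.3.1 does not say so.

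**Conclusion.** The mixing follows from the text and needs no assumption: up to 84 of 168 days in the placebo and 16mg columns are on 160mg or 320mg. The dilution depends on a drug or dose effect on risk, and with no effect there is nothing to dilute. Its size rests on assumed constant rates, because the documents give none. A rate ratio of 2.0 reads between 1.67 and 1.33 as the available post-switch time rises from 25% to 100%.

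A reader might infer that the interim report conceals the drug-placebo difference or the dose trend. The documents do not support this, since the up-to-Week-12 table shows the randomized comparison essentially before any switch. A reader might also infer that dose selection rests on the diluted table. SAP 4.3.1 ties dose selection to the exposure-response of ACR and PASI, and its other aim is to evaluate the Double-Blind data. No final estimate or test is affected. What remains is a mislabelled supplementary table that was produced as planned for adverse events and should be corrected or annotated.

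**What to change.** In the up-to-Week-24 safety tables of SAP 4.3.1:

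1. Count placebo and 16mg subjects under their Baseline arm only until the first Dose-Blind injection.
2. Count their later events in one pooled column, *switched to bimekizumab at Week 12*, with 160mg and 320mg combined. Check this against the study's blinding plan, which is a separate document.
3. Give subject-years at risk and exposure-adjusted rates for every column, by the method of SAP 10.2.2, so that 12-week and 24-week crude percentages are not set side by side. Take time to first event as that section defines it in words, because the equation it cites (40) is the duration of an adverse event. For laboratory values summarized by visit, moving the post-switch visits to the pooled column is enough.
4. Name the up-to-Week-12 table as the placebo comparison.

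For interim tables already issued, add a footnote that the placebo and 16mg columns include post-switch time on 160mg or 320mg.

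The cost is a wording change, one extra column and an exposure calculation that the interim does not now include. No new data are needed.
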